## 5. Study design

The study will use a quasi-experimental design, with data collection taking place in three different stages: 1) Baseline data collection to assess comparability of facilities, service quality and client's behaviors, 2) Facility-based endline data collection and 3) Community-based endline survey (**Figure 1**).

The study will use mixed data collection methods including: 1) facility assessment; 2) provider survey; 3) case observations (namely ANC visits, child visits [both sick child and immunization], and counseling sessions), 4) client interviews and 5) in-depth interview with Program Managers and Field Supervisors.

Figure 1: Impact Evaluation Design

## 6. Overview of intervention and comparison facilities

The program interventions are implemented in 8 NGO-run urban health facilities, 4 of which are operated by Radda and 4 of which are operated by Marie Stopes. These 8 facilities will serve as the intervention group. The comparison group will also consist of 8 NGO-run urban health facilities, but these are run by Nari Maitree and Shimantik, which operate under the Urban Primary Health Care Services Delivery Project. The list of facilities in the intervention and comparison groups is presented in **Appendix 1**.

## 7. Sample size and power calculation

Sample size has been estimated based on the baseline prevalence of the primary outcomes, the expected change after intervention, the power to detect those differences at 0.80, and a level of significance of 0.05. The outcomes used for sample size calculation were quality of nutrition service delivery (including provision of counseling on diet and breastfeeding practices). The sample size was calculated at 2 levels: provision of services (measured through case observation) and receipt of services (measured through client interviews).

Based on data from baseline assessment, we calculated the prevalence for expected outcomes, and the intra-cluster correlations (ICCs). We estimated that a minimum sample size of 1200 clients per group during the first phase of the endline survey conducted at the facilities would have at least 80 percent power to detect a difference of 10-19 percentage points (pp) between intervention and comparison groups in the changes over time for different context-specific outcomes (**Table 2**), e.g. maternal counselling during pregnancy and IYCF counselling to caregivers of young children. During the follow up in the communities, we expect a ~30-33% loss from the original sample, and thus estimate we will collect information from 65-70%. We expect that this will give us enough power to detect changes in context-specific behavioral outcomes. Instead of separating the sample for ANC and child contacts, we will pool them to examine context-appropriate behavior such as pregnant women with dietary diversity/IFA and calcium consumption and caregivers with age-appropriate child feedings. These detectable differences are of reasonable public health significance and based on the previous experience from evaluation of the A&T Bangladesh maternal nutrition study [7].

For facility readiness and provider knowledge, with the sample size of 8 facilities and 40-64 providers in this group, we will mainly report the descriptive analyses between two groups, but not report statistical test due to small sample size.

Table 2. Sample size and power calculation

	Control group, endline 	Expected difference	Treatment group, endline	Power	ICC	Alpha	Sample size per group
Quality of services (measured through case observation)							1200
Counseling on diet	68.0	19.0	87.0	0.8	0.103	5	
Counseling on breastfeeding	71.6	17.1	88.7	0.8	0.09	5	
Context-appropriate behavioral outcomes (measured through client interview)							1200 at facility-based endline 800 (67%) at community-based endline
Consume 100+ IFA	54.5	9.5	64.0	0.8	0.001	5	
Dietary diversity during pregnancy	74.0	9.5	83.5	0.8	0.009	5	
Early initiation of breastfeeding	32.8	13.5	46.3	0.8	0.024	5	

Data from AINNS study [8]

Data from Bangladesh DHS 2014 [9]

We expect to see no difference in the control group at baseline vs. endline.

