**Table 7. Modules included in client interview**

Module	Topic	Description
1	Background and demographic characteristics	Factors such as age, education, religion, living standard, etc., have influences on client's behaviors, including MIYCN practices and service utilization. This data also provides information about outside factors, including the COVID-19 pandemic that may constrain mothers' ability to benefit from services. Data will be collected on household information, socioeconomic status, income and expenditure, and the education and other characteristics of the women and their husbands.
2	Obstetric history	This section information on the woman's pregnancy history including complications, total parity and age at first parity.
3	Previous ANC care/care seeking for the child	This will include receipt and consumption of IFA and calcium and antenatal care and counselling during current pregnancy for pregnant women. Mothers of sick children will also be asked about postnatal services, morbidity and care of children, and vaccination history. This will help to assess if exposure to

Module	Topic	Description
		intended program is occurring as expected and assess impact trends by levels of exposure to interventions.
4	MN Dietary intake/IYCF practices	Respondents will be asked to recall what they ate (ANC clients) or what they fed their children (mothers of sick children) on the previous day. Mothers of sick children will also be asked other questions on IYCF practices and behaviors. This will provide information on MIYCN behaviors.
5	Current MIYCN knowledge and perceptions	Data on mothers' MIYCN knowledge and perceptions can be used to assess trends in impact indicators and to identify pathways to positive behavior change. Questions on self-efficacy will be included.
6	Social desirability	This is a factor that may affect the woman's ability to change behaviors and practices around MIYCN.
7	Food security	Questions on food security will be included as they are related to the respondent's ability to follow counselling on diet for herself and her children.
8	Decision-making power and mental health	Decision-making power and mental health are also related to the woman's ability to change behaviors and practices around MIYCN.

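### Table 2 sizes three single-client-type behaviour outcomes at 800 per group where Table 4 plans 400, and the text and footnotes disagree on where its inputs came from

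*Combined protocol and SAP*

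**What the plan says.** **Source of inputs.** The text of Section 7 states: "Based on data from baseline assessment, we calculated the prevalence for expected outcomes, and the intra-cluster correlations (ICCs". Under Table 2, footnote 1 (quality rows) reads "Data from AINNS study [8" and footnote 2 (behaviour rows) reads "Data from Bangladesh DHS 2014 [9".

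**Sample size.** Section 7 sets power at 0.80 and alpha at 0.05. It says "The outcomes used for sample size calculation were quality of nutrition service delivery", with 1200 clients per group at the facility-based endline. For the behaviour block (100+ IFA tablets, dietary diversity during pregnancy, early initiation of breastfeeding) the Table 2 sample-size cell reads "1200 at facility-based endline 800 (67%) at community-based endline". Power is printed as 0.8 in all five rows.

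**Who supplies each behaviour outcome.** Table 7 in Section 9.4 lists "receipt and consumption of IFA and calcium and antenatal care and counselling during current pregnancy for pregnant women". On diet and feeding, respondents "recall what they ate (ANC clients) or what they fed their children (mothers of sick children" on the previous day, and the other infant-feeding questions go to the mothers. Table 4 plans 400 ANC and 400 IMCI client interviews per group at endline.

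**Pooling.** Section 7 adds: "Instead of separating the sample for ANC and child contacts, we will pool them to examine context-appropriate behavior". It gives maternal diet, IFA and calcium as the behaviours for pregnant women, and child feeding as the behaviour for caregivers.

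**The concern.** Each of the three behaviour rows describes one kind of client. Dietary diversity during pregnancy and IFA intake come from pregnant women; early initiation comes from mothers of infants. If 800 is read as each row's denominator, it is twice what Table 4 provides, and power judged at 800 is too favourable. A null result on one of these outcomes would then be read against a power figure that its actual denominator does not support.

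The second issue is traceability. The prevalences and ICCs drive every row of Table 2. The text places their origin in this study's baseline, which Section 11 shows in the field in late 2019 and early 2020. The footnotes place it in two external datasets whose references are dated 2016, one of them for the 2014 DHS. Nothing reconciles the two, and the footnotes do not say whether they cover the prevalence, the ICC or both.

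**Working it through.** **Inputs.** Prevalences, differences and ICCs: Table 2. Facilities: 8 per group (Section 6). Alpha 0.05 and target power 0.80 (Section 7). Group sizes: 1200 and 800 (Table 2), 400 per client type (Table 4). Expected follow-up: 65-70% (Sections 7, 8 and 9.4). Assumed, because not stated: two-sided test, equal cluster sizes, the facility as the cluster for the Table 2 ICCs, and the same ICC at the smaller cluster size.

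**Formulas.** The contrast is at endline only, following Table 2's layout and its footnote 3 (no change expected in the control group).

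- Cluster size m = n/8; design effect DE = 1 + (m - 1) x ICC.
- SE = sqrt[(p0q0 + p1q1) x DE/n]; power = Phi(d/SE - 1.96) (unpooled variance).
- Pooled check: SE0 = sqrt[2 x pbar x qbar x DE/n]; power = Phi((d - 1.96 x SE0)/SE), where pbar is the mean of p0 and p1.
- Detectable difference: the d that gives 80% power with p1 = p0 + d (unpooled).

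**Step 1: reproduce the plan's own figure.** Quality rows, n = 1200, m = 150.

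- Diet counselling (68.0 v 87.0, ICC 0.103): DE = 1 + 149 x 0.103 = 16.35; SE = sqrt(0.3307 x 16.35/1200) = 0.0671; power = Phi(0.190/0.0671 - 1.96) = 80.8% (pooled 79.3%).
- Breastfeeding counselling (71.6 v 88.7, ICC 0.09): DE = 1 + 149 x 0.09 = 14.41; power 80.8% (pooled 79.5%).

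The method reproduces 1200 per group and 0.80 for both rows.

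**Step 2: behaviour rows at 800 and at 400 per group.**

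| Row | p0 v p1 (%) | ICC | Power at 800 (m = 100) | DE at 400 (m = 50) | Power at 400, unpooled / pooled | Detectable v planned (pp) |
|---|---|---|---|---|---|---|
| 100+ IFA | 54.5 v 64.0 | 0.001 | 96.0% | 1.05 | 76.5% / 76.2% | 9.9 v 9.5 |
| Dietary diversity | 74.0 v 83.5 | 0.009 | 92.5% | 1.44 | 78.7% / 78.3% | 9.6 v 9.5 |
| Early initiation | 32.8 v 46.3 | 0.024 | 85.9% | 2.18 | 76.2% / 75.6% | 14.2 v 13.5 |

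The IFA row in full: DE = 1 + 49 x 0.001 = 1.049; SE = sqrt(0.4784 x 1.049/400) = 0.0354; power = Phi(0.095/0.0354 - 1.96) = 76.5%. With no clustering at all it is 78.4%, so this shortfall does not depend on the ICC.

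**Step 3: the stated follow-up range.** Table 4 has 600 observed clients per type per group; 65-70% of 600 is 390-420. Over that range power is about 75-78% (IFA), 78-80% (dietary diversity) and 75-77% (early initiation).

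**Step 4: the pooled indicator.** A composite scored in all 800 clients is a different outcome from any of the three rows. It needs its own control prevalence, expected difference and ICC. Table 2 gives none of these, so its power cannot be calculated from the plan.

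**Step 5: sources.** Text: baseline assessment. Footnote 1: AINNS. Footnote 2: DHS 2014. Taken at face value, these cannot all describe the origin of the same figures.

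**The case against.** **On the behaviour rows.** The miss is 1 to 4 points on outcomes that Section 4 lists as secondary. Table 2 prints power to one decimal, and 76.5%, 78.7% and 76.2% all round to 0.8. The 800 may be a block total (400 ANC plus 400 IMCI) and not each row's denominator. Section 7 ties its explicit claim of at least 80% power to the 1200 facility-endline clients, and promises only adequate power for the community round. At 600 per type the same formula gives 90%, 88% and 83%. The planned analysis of covariance (Section 10) could also gain precision that an endline contrast leaves out.

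Much of this stands. The shortfall is modest, and dietary diversity is essentially at 80% with 420 women. But Section 9 assigns behaviour change to the community round, so 400 is the relevant count. If 800 is a block total, the table should say so. Table 2 claims no gain from covariance adjustment and gives no baseline correlation from which to credit one.

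**On sources.** The AINNS reference is titled an initial assessment, so the text's baseline assessment might loosely mean that. The DHS footnote would still be unexplained.

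**Stronger readings that a reader might infer.** One is that the counselling-quality rows are fragile because a slightly higher ICC takes them below 80%. That is not a defect: a sample sized for 80% has no margin by construction, and the rows reproduce. Another is that the cluster unit is undefined. Section 7 does not name it, but Section 10 plans random effects for clustering at facility level, and the quality rows reproduce with 8 facilities of 150. A third is that the ICCs are wrong. The conflict between text and footnotes shows only that their stated origin needs correcting.

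**Conclusion.** The point holds in two limited parts.

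1. Table 2's 800 per group is not the denominator for its three behaviour rows. At Table 4's 400 per client type all three fall below the stated 0.80, by about 1 to 4 points, and the detectable differences exceed the planned ones by about 0.1 to 0.7 percentage points. The pooling plan leaves this open because the pooled outcome has not been sized.
2. The text and footnotes give conflicting origins for the Table 2 inputs.

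The power figures rest on the assumptions listed with the inputs and on an endline contrast without covariance adjustment. The 400 for IFA is an inference: Table 7 describes recall for the current pregnancy of pregnant women. Early initiation is not named in Table 7 and is placed with mothers of infants as an infant-feeding practice. If either were also collected from the other client type, its denominator would be larger. The quality rows, on which the study was sized, are not in error.

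**What to change.** - In Table 2, give 400 per group for the behaviours that apply to one client type, and restate their power or detectable difference, preferably over 390-420 to match the stated follow-up.
- If the pooled context-appropriate indicator is to be analysed, define it and add a row at 800 with its own prevalence, expected difference and ICC.
- Give one source for each prevalence and ICC, and correct whichever of the Section 7 text or the footnotes is wrong.

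This is a revised table and a sentence or two of text, with no added enrolment. The price is that the stated power for the behaviour rows becomes slightly less favourable.

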**Table 4. Sampling clients at intervention and comparison facilities**

Levels		Intervention facilities (n=8)	Comparison facilities (n=8) 
Baseline	Case observation		
	ANC	600	100
	IMCI	600	100
	Client interview		
	ANC	400	70
	IMCI	400	70
	Total:	2,000	340
Endline	Case observation		
	ANC	600	600
	IMCI	600	600
	Client interview		
	ANC	400	400
	IMCI	400	400
	Total:	2,000	2,000

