### 9.3. Case observation

Case observations will be conducted in both intervention and comparison health facilities at baseline and endline. The observation checklists will be used to observe the service content as well as interactions between the client and provider. Specifically, the counseling observation checklist will be developed based on the MIYCN service delivery package guidelines. In addition to content coverage, a checklist will also be used to assess counselors' skills and counseling processes. Items from this checklist will be used to measure the quality of the counseling session. At the end of the counseling session, a short exit interview (5-10 minutes) will be used, to ask the respondents about services received during that visit, nutrition information provided, and their satisfaction with the services they received

At baseline, 1400 case observations (1200 in intervention and 200 in control groups) were conducted, along with basic client information. During the facility-based endline, 1200 case observations will be conducted in each group. We expect to have 15 days of observations in each facility, 10 observations per day: 5 ANC visits (include counseling), 5 child or immunization visits (include counseling). Total:  $10*15 \text{ days}*8 \text{ facilities}=1200$  observations in interventions and 1200 in comparison facilities.

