## 10. Analysis plan

All statistical analysis using quantitative data will be done using Stata 17. Data collected at baseline will be analysed to examine the balance on key baseline characteristics between intervention and comparison groups. Statistical testing for differences between the two groups will be done using a random effects regression, taking into account the clustering of errors within and across health facilities.

Appropriate variables will be created for each set of outcomes. For quality of care, the key indicators will be facility readiness, knowledge of healthcare providers, nutrition counselling service scores, and clients' utilization of and satisfaction with MIYCN services. For behaviour outcomes, the key indicators will be maternal nutrition practices (dietary diversity, IFA and calcium consumption) and age-appropriate IYCF practices. Impacts on these outcomes will be estimated using analysis of covariance which is an accepted impact evaluation analysis approach that is widely used. Further adjustment for geographic clustering at the facility level will be done using random effects.

Qualitative interview data (transcripts) will be organized and analyzed using software such as NVivo, Excel or others as appropriate. Data analysis will identify the emerging deductive and inductive themes that emerge from the interviews under 4 study domains: intervention impact pathway, uptake of interventions, programmatic performance, and supportive supervision activities. Categories and subcategories under these domains will be identified and defined (conceptualized) to feed into a narrative complementing the quantitative data results.

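### Section 7 claims 80% power for a difference in changes over time, but Table 2 carries no baseline sample sizes, the behavioural rows fall short on that contrast, and Section 10 plans a different analysis

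*Combined protocol and SAP*

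**What the plan says.** - **Power claim (Section 7).** The endline sample is said to give "at least 80 percent power to detect a difference of 10-19 percentage points (pp) between intervention and comparison groups in the changes over time".
- **Table 2.** The columns are endline control rate, expected difference, endline treatment rate, power (0.8 in every row), ICC, alpha and sample size per group. The counselling rows carry 1200. The behavioural rows carry 1200 at the facility round and "800 (67%) at community-based endline". Footnote 3 assumes that the control rate does not move between rounds.
- **Baseline sizes.** Section 9.3 reports: "At baseline, 1400 case observations (1200 in intervention and 200 in control groups) were conducted". Table 4 gives baseline interviews of 400 ANC plus 400 IMCI in the intervention group, but 70 plus 70 in the comparison group. At endline it plans 400 plus 400 in each group.
- **Analysis (Section 10).** "Impacts on these outcomes will be estimated using analysis of covariance", with facility random effects. No baseline covariate and no group-by-time term is named.
- **Denominators.** Section 7 says: "Instead of separating the sample for ANC and child contacts, we will pool them to examine context-appropriate behavior". Table 7 collects "receipt and consumption of IFA and calcium and antenatal care and counselling during current pregnancy for pregnant women", and asks respondents to "recall what they ate (ANC clients) or what they fed their children (mothers of sick children").
- **Sources.** The Section 7 text attributes prevalences and ICCs to the baseline assessment. Table 2 footnotes 1 and 2 cite an earlier nutrition-services evaluation and the 2014 national demographic and health survey.

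**The concern.** Three parts of the plan should describe one effect: the power sentence, the table behind it, and the impact model. Here the sentence describes a difference in changes, the table holds endline inputs, and the model is analysis of covariance.

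Footnote 3 makes the expected difference in changes equal in size to the expected endline difference. It does not remove the sampling error of the baseline, which is large because the comparison baseline is about one sixth the size of the intervention baseline.

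If impact is reported as Section 7 describes, a null result on a behavioural outcome could be read as coming from an adequately powered comparison when it did not. If Section 10 is followed, the power sentence describes the wrong contrast.

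**Working it through.** **Inputs.** Proportions and ICCs are from Table 2, with 8 facilities per group (Section 6) and sample sizes from Table 4 and Section 9.3. Alpha is 0.05, taken as two-sided. Three assumptions are needed: the intervention baseline rate equals the control rate; the between-round correlation of facility levels, r, is not given and runs from 0 to 1; and power = Φ(difference/SE − 1.96).

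**Step 1. Table 2 as an endline-only comparison.** Variance = Σ p(1−p)/n × [1 + (n/8 − 1)ICC] over the two groups.

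- Diet counselling, n = 1200: (0.2176 + 0.1131)/1200 × (1 + 149 × 0.103) = 0.004505. SE = 0.0671 and 0.19/0.0671 = 2.83, so power is 0.808.
- Breastfeeding counselling: 0.808 by the same route.

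A pooled-variance form gives 0.793 and 0.795. Either way the printed 0.8 is recovered without a baseline term, although the plan does not state its formula.

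| Row | n = 800 | n = 400 | n per group for 80% |
|---|---|---|---|
| IFA | 0.960 | 0.765 | 438 |
| Dietary diversity | 0.925 | 0.787 | 420 |
| Early initiation | 0.859 | 0.762 | 500 |

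**Step 2. The contrast Section 7 names.** With q = p(1−p), s = ICC × q, I and C the intervention and comparison groups, and 1 and 0 endline and baseline:

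Variance = (1−ICC) Σ q/n over the four cells + [s_I1 + s_I0 − 2r√(s_I1·s_I0) + 2s_C(1−r)]/8.

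IFA example, baseline 800/140 and endline 800/800:

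- Sampling part: 0.999 × (0.000310 + 0.001771 + 0.000288 + 0.000310) = 0.002677.
- Facility part: 0.000122 at r = 0, about 0 at r = 1.
- SE = 0.0529 to 0.0517, so power is 0.44 to 0.45.

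The term 0.001771 is the 140 comparison interviews, 66% of the sampling part.

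| Row | Planned difference | Power, 800/140 then 800/800 | Detectable (2.80 × SE) | Power, 400/70 then 400/400 | Detectable |
|---|---|---|---|---|---|
| IFA | 9.5 pp | 44-45% | 14.5-14.8 pp | 25% | 20.5-20.7 pp |
| Dietary diversity | 9.5 pp | 43-56% | 12.6-14.9 pp | 28-32% | 17.8-19.5 pp |
| Early initiation | 13.5 pp | 47-79% | 13.7-20.0 pp | 35-50% | 19.3-24.2 pp |

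With 400 in all four cells, power would be 47-49%, 47-62% and 48-82%. Differencing itself therefore costs power, and the small comparison baseline costs more.

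Counselling rows (baseline 1200/200, endline 1200/1200): 43% for both at r = 0, and 66% (diet) and 64% (breastfeeding) at r = 0.5. They reach 80% from r of about 0.69 and 0.72, and exceed 99% at r = 1.

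**Step 3. The analysis Section 10 names.** Section 10 names no covariate, so I assumed adjustment for facility baseline means. The common slope is cov(baseline, endline facility mean)/var(baseline facility mean), with no penalty for estimating it from 16 facilities.

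| Row | 800/140 | 400/70 |
|---|---|---|
| IFA | 96% | 76% |
| Dietary diversity | 93-95% | 79-80% |
| Early initiation | 86-95% | 76-83% |

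The counselling rows are at 81% or more.

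**Step 4. Which n applies.** The 800 is 400 ANC plus 400 IMCI clients. IFA in the current pregnancy and maternal diet recall come from ANC clients, and early initiation from mothers. Pooling can support a combined context-appropriate indicator, but it does not give 800 respondents to any of these three rows.

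**The case against.** The strongest reply is that the shortfall belongs to an estimator Section 10 does not plan. Under analysis of covariance the pooled behavioural rows run at 86-96%, and even at 400 per group they sit within a few points of 80% and round to the printed 0.8. That stands, and it limits the point: the shortfall is against the contrast Section 7 names. It does not remove the conflict between the two sections, and at 400 the endline-only rows still miss the stated minimum of 80%.

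Other objections carry part of their weight:

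- **Facility-round sizes.** The power sentence concerns 1200 clients per group; for the community round the prose promises only enough power. With 1200/200 at baseline and 1200 per group at endline, early initiation runs from 53% to 92%, passing 80% at r of about 0.75. IFA (57-60%) and dietary diversity (53-72%) still fall short. Table 2 nevertheless prints 0.8 beside the 800, and Table 4 plans interviews at that size.
- **Comparison baseline.** Its 65-68% share of the behavioural rows' variance is of sampling variance only. In total variance at r = 0 (800/140) it is about 63% for IFA, 48% for dietary diversity and 30% for early initiation. For the counselling rows (1200/200) it is 9-10%, so facility variation dominates there.
- **Counselling denominators.** These rows were kept pooled because the plan does not define their denominators. Splitting them to 600 per group lowers endline-only power to 79% and 78%.
- **Normal approximation.** It flatters a 16-facility design. A t reference with 14 df puts the endline-only counselling rows near 75%.
- **Footnote 3.** It does supply a control baseline rate. What Table 2 lacks is the baseline sample sizes, the intervention baseline rate and the between-round correlation.

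**Conclusion.** The point holds. Section 7, Table 2 and Section 10 do not identify one effect, and that conclusion needs no modelling assumption.

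On the difference in changes with Table 4 interview sizes, every behavioural row is below 80% at any r. The miss is wide for IFA and dietary diversity, while early initiation comes within about a point of 80% at r = 1 with pooled numbers. The counselling rows reach 80% only if facility levels are strongly correlated between rounds. These figures rest on Table 2 rates and ICCs, equal baseline rates in the two groups and a normal approximation.

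The printed 800 is the wrong denominator for the three behavioural rows, and the stated source of the inputs conflicts with the footnotes. This should be fixed. It does not show that the Section 10 model is materially underpowered.

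**What to change.** Name one estimand in Sections 7 and 10.

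- **If it is the difference in changes:** recompute Table 2 with the Table 4 baseline and endline sizes, the trial's own 2019-20 baseline prevalences and facility ICCs, and a stated range of between-round facility correlation. Make Section 10 estimate that contrast.
- **If it is an endline or baseline-adjusted comparison:** remove the reference to changes over time from the power sentence, label Table 2 accordingly, and name the baseline covariate in Section 10.
- **In either case:** print about 400 per group for outcomes defined only in ANC clients or only in mothers, and keep 800 only for a defined pooled indicator. Reconcile the source statement with the footnotes, and restate power and detectable difference row by row.

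The cost is a recalculation and edits to Section 7, Table 2 and one paragraph of Section 10. No extra clients are needed, but some stated power and detectable differences will become less favourable.

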- Pregnant women who are visiting the health facilities for ANC visits (at least twice during her pregnancy, around half of clients)
- Mothers with children <12 months of age who are visiting the health facilities for health check-ups or vaccination

Exclusion criteria:

- Pregnant women with severe illness or complications
- Mothers with severely ill children

For the assessment of **impacts** of standardized and upgraded MIYCN counseling service on coverage and behavior changes we will identify each facility's catchment area and find women in the community who accessed services at those health facilities to sample 1600 facility clients (PW and RDW) to interview (**Table 4**). During the facility interviews, we will seek their consent to be interviewed at home for the community

interview at a later time. Follow-up with clients for the community interview was conducted within 3 months following the facility interview at baseline. At endline, facility clients will be visited within one month to conduct the community interview. We expect that we will be able to follow 65-70% of these women. By doing so, we ensure that our clients will have at least one visit in the evaluation facilities (both intervention and control areas). We can track the number of clinic visits and thus conduct the dose response analysis.

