## 9. Data collection methods

The survey will use mixed data collection methods including: 1) facility assessment; 2) provider survey; 3) case observations (include ANC visits, child visits [both sick child and immunization], and counseling session), 4) client interviews, and 5) in-depth interview with Program Managers and Field Supervisors. At endline, we will have two rounds of client interviews: one round at the health facility to measure utilization and one round to follow up clients (within a months later) in the community to measure behavior changes.

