### 9.4. Client interview

Clients who are observed at facilities will also be interviewed in their homes as a follow-up to measure behavior change (**Table 7**). During the facility interviews, we will seek their consent for the community interview to contact them to set up home visit within one month. We expect that we will be able to follow 65-70% of these women. By doing so, we ensure that our clients will have at least one visit in the evaluation facilities (both intervention and control areas). We can track the number of facilities visits and thus conduct the dose response analysis.

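### Behavior outcomes are assigned to a home interview expected to reach 65-70% of clients, and the analysis plan has no check for selective loss

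*Combined protocol and SAP*

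**What the plan says.** Section 7 sets "a minimum sample size of 1200 clients per group during the first phase of the endline survey conducted at the facilities". It then states "During the follow up in the communities, we expect a ~30-33% loss from the original sample". Table 2 carries this through for the behavior rows as "1200 at facility-based endline 800 (67%) at community-based endline". Section 8 gives the matching total, "to sample 1600 facility clients (PW and RDW) to interview", which is 800 per group.

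Section 9 describes two rounds of client interviews at endline: one at the facility for utilization, and "one round to follow up clients (within a months later) in the community to measure behavior changes". Section 9.4 repeats the expected retention: "We expect that we will be able to follow 65-70% of these women". Consent for the home visit is sought during the facility interview (Sections 8 and 9.4).

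At the facility, Section 9.3 plans 1200 case observations per group at endline. Once counseling is over, "a short exit interview (5-10 minutes) will be used, to ask the respondents about services received during that visit", along with nutrition information given and satisfaction.

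Section 10 says "Impacts on these outcomes will be estimated using analysis of covariance", with facility random effects. It names no analysis population for the home round, no comparison of followed with lost clients, no weighting or imputation, and no sensitivity analysis for the loss. The only comment on the loss is in Section 7, where the remaining sample is expected to give enough power.

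**The concern.** Losing a third of the sample does more than cut precision. A regression on home-interview outcomes drops anyone without a home interview, so the behavior effects would describe the women reached. If those women differ from the lost women in diet, supplement use or infant feeding, and differ by more in one arm than in the other, the between-arm effect is biased. A larger sample does not remove that bias.

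There are reasons not to assume equal loss processes in the two arms. Consent is sought around the visit whose counseling content the program changes. Intervention facilities have additional community workers (Table 3). The home-visit window also changed between rounds, from three months at baseline to one month at endline (Section 8), so retention may differ by round as well. As written, the plan has no step that would reveal any of this, although some data on every observed client are recorded at the facility.

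**Working it through.** **Plan's own figure.** 10 observations × 15 days × 8 facilities = 1200 per group (Section 9.3). 1200 × (1 − 0.33) = 804, and 800/1200 = 66.7%, so the 800 (67%) in Table 2 reproduces.

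**Bias from complete-case analysis.** In one arm, let r be the share followed and g the outcome prevalence in followed minus lost clients.
- The prevalence in all clients is r × P(followed) + (1 − r) × P(lost), so the followed-only prevalence exceeds it by (1 − r) × g.
- The bias in the effect is therefore (1 − r_T) × g_T − (1 − r_C) × g_C, for treatment (T) and comparison (C).

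**Equal follow-up, gaps differing by 10 pp (assumed).** Targets are from Table 2: 9.5 pp for 100+ IFA and dietary diversity, 13.5 pp for early initiation of breastfeeding.

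| Followed | Shift | Share of 9.5 pp | Share of 13.5 pp |
|---|---|---|---|
| 70% | 0.30 × 10 = 3.0 pp | 32% | 22% |
| 67% | 0.33 × 10 = 3.3 pp | 35% | 24% |
| 65% | 0.35 × 10 = 3.5 pp | 37% | 26% |

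The shift is proportional to the assumed difference. At 33% loss, 5 pp gives 1.7 pp and 15 pp gives 5.0 pp.

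**Equal gaps.** With equal follow-up the shift is zero. With 65% followed in one arm and 70% in the other, a shared gap of 20 pp gives 0.35 × 20 − 0.30 × 20 = 1.0 pp.

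**Accounting for the whole 9.5 pp.** The gaps would have to differ by 9.5/0.35 = 27 pp to 9.5/0.30 = 32 pp.

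**Precision cost of weighting.** The effective sample is n/(1 + CV²), where CV is the coefficient of variation of the weights. The documents give no CV, so 0.2 to 0.5 is assumed: 800/1.04 = 769 and 800/1.25 = 640.

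Power uses Table 2's rates and ICCs, a two-sided 5% test (sidedness is not stated), a normal approximation, and design effect 1 + (m − 1) × ICC with m = 800/8 = 100.

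| Outcome | Power at 800, unweighted | CV 0.2 | CV 0.5 |
|---|---|---|---|
| 100+ IFA | 95.9% | 95.2% | 91.1% |
| Dietary diversity | 92.3% | 91.3% | 85.7% |
| Early initiation | 85.4% | 84.1% | 76.9% |

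If an outcome applies to one client type only (400 per group, Table 4), unweighted power is 76.2%, 78.3% and 75.6%, falling to 66.6%, 68.8% and 66.0% at CV 0.5.

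**Baseline model size.** Table 4 has 200 comparison clients observed and 140 interviewed, so about 60 not followed. Facility (7 terms), client type (1), time interval (3), counseling (1) and satisfaction (1) make 13 terms, and 60/13 is fewer than 5 losses per term.

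**The case against.** The case against has several parts, and much of it stands.

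- **Complete-case analysis is inferred.** Section 10 never states it. Table 2 sets 1200 at the facility beside the behavior outcomes, and Table 7, module 9, says the same tools serve the follow-up round, so some practice items may also be taken at the facility. Sections 8, 9 and 9.4 nevertheless assign behavior to the home round.
- **Facility data may not cover everyone.** A reader might infer that every client has an exit interview and background data. Section 9.3 mentions basic client information only for the baseline observations and places the exit interview after the counseling session. Table 1 says comparison facilities offer counseling only where a counselor is available. Socioeconomic items sit in the client interview (Table 7). The adjustment may therefore be weak.
- **Direction is unknown.** A reader might infer that satisfied women are retained and that the bias favours the program. The documents give no reasons for loss and do not separate refusal from failure to locate.
- **Stable selection may cancel.** Section 7 speaks of changes over time, and baseline interview ratios are similar (800/1200 and 140/200). Selection that is constant within an arm would largely cancel in a change comparison. That is a fair limit, but Section 10 does not say how baseline enters the model, and the changed window makes constancy uncertain.
- **Some non-interview may be by design.** Section 8 and Table 4 set 800 interviews per group as a target, and random subsampling would cause no bias. Section 7, however, calls the shortfall a loss.

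The primary counseling-quality outcomes measured by case observation are not affected.

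**Conclusion.** The point holds in a limited form. The secondary behavior outcomes are assigned to a round expected to miss 30-35% of clients, the plan treats this only as lost power, and nothing in Section 10 would detect or address selective loss. Each 10 pp between-arm difference in the followed-minus-lost gap moves the effect by 3.0 to 3.5 pp, roughly a third of a 9.5 pp target and about a quarter of the 13.5 pp target. With equal gaps the shift is close to zero.

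The gaps are assumptions, and the documents support neither a size nor a direction. They do not support a claim that the behavior effects are biased toward the program, or that selection could readily account for the whole effect, since that would take a gap difference of 27 to 32 pp. This is a recommended improvement to the analysis plan and does not undermine the primary results.

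**What to change.** In Section 10:

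1. Tabulate follow-up by arm, facility and round, separating refusal, failure to locate and any planned subsampling. Compare followed with lost clients on the facility-stage data.
2. Keep the unweighted estimates and report beside them a sensitivity analysis weighted by the inverse probability of follow-up. At endline, fit the follow-up model by arm on variables available for all observed clients: facility, client type, time interval, observed counseling content, and exit-interview satisfaction where recorded.
3. At baseline, use a reduced or pooled follow-up model, because about 60 lost comparison clients cannot support a separate model with 13 terms.
4. Reconcile Table 2, Section 9, Section 9.4 and Table 7 (module 9) on whether behavior items are also collected at the facility. If they are, they belong in the comparison and the weights.

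The cost is plan wording and a few logistic models. The weighted intervals will be somewhat wider (effective 640 to 769 of 800 per group at assumed CVs of 0.5 to 0.2), and early-initiation power could fall below 80% at the heavier weights. Weighting removes only loss explained by measured variables, so a close match between weighted and unweighted results would be reassuring but not conclusive.
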